## 1.0 Objectives

### 1.1 Study Objectives

Describe the purpose, specific aims or objectives. State the hypotheses to be tested.

In this study, we propose a prospective trial to determine if contrast enhanced ultrasound (CEUS) is non-inferior to CT or MRI in patients with hepatocellular carcinoma (HCC) following transcatheter arterial chemoembolization (TACE) treatments, in a U.S. population, using Lumason contrast agent. This would be the largest trial to date examining this patient population in the U.S.

The primary objective of our study is to estimate the sensitivity and specificity of the CEUS (Research Timepoint 1) and evaluate for non-inferiority between CEUS and the clinical gold standard of CT/MRI using the Liver Reporting & Data System (LIRAD). We will be assessing the presence of treated or residual tumor, new sites of disease, and portal vein thrombus. Patient factors, such as BMI, underlying liver disease type, alpha fetoprotein level, and size of liver will be recorded. If findings of metastatic disease external to the liver are identified on CT or MRI and not seen on CEUS, they will be recorded.

CEUS, like regular ultrasound, only images specific organs and cannot identify necessarily metastatic disease, as ultrasound cannot image bones and lungs for this purpose.

The second objective of the project will compare the CEUS with a second, standard of care, follow-up CT or MRI (performed 2-4 months later [Research Timepoint 2]). CT can have false negatives due to ethiodol obscuring subtle, early disease and it is possible that CEUS could identify residual disease earlier compared to the gold standards, but would be characterized as a false positive if compared only to the initial imaging (Timepoint 1). This follow-up will evaluate for false positives or negatives on any of the modalities.

The third objective of the project will evaluate patient subjective data in regards to imaging modality preference and possible effects on compliance. The survey will be administered at the conclusion of Timepoint 1 and will include questions about anxiety, comfort, compliance, and modality preference, graded on a Likert scale.

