## 2.0 Background

### 2.1 Scientific Background and Gaps

Describe the scientific background and gaps in current knowledge.

For clinical research studies being conducted at Penn State Health/Penn State College of Medicine, and for other non-PSH locations as applicable, describe the treatment/procedure that is considered standard of care (i.e., indicate how patients would be treated in non-investigational setting); and if applicable, indicate if the study procedure is available to patient without taking part in the study.

Contrast-enhanced ultrasound (CEUS) has been in use globally for decades, but has only recently been approved for clinical use in the U.S. The accuracy of CEUS is similar to MRI and CT scans in establishing the diagnosis of hepatocellular carcinoma (HCC) in at risk-patients (1) and is being utilized with greater frequency to make this important diagnosis in patients with cirrhosis in the U.S.

One of several treatments for HCC is transcatheter arterial chemoembolization (TACE), with follow-up in 2-4 months - typically with either a CT or MRI. The efficacy of CEUS in the post-TACE HCC population has been evaluated in the literature (2-14) , which shows that it is reliable in diagnosing this entity via CEUS. However, some of the articles are with contrast agents not available in the US, some are in different patient populations than is common in the US (for example, hepatitis B is less common in the US than alcoholic cirrhosis, but the converse is true in most of the references studies, which were performed internationally) and should be replicated in the US population, and many of the articles were retrospective.

Over the last few years there has been slowly growing literature available in the U.S. patient population, in the form of case reports (15) or small (fewer than 20 patients) prospective studies (16, 17). But even these studies are not comparable with current CEUS practices, as both Shaw and Nam's small studies used Definity, a contrast agent approved in the U.S. that has low, but higher adverse events than Lumason (18) contrast agent, which is the standard contrast that is utilized at Penn State Milton S. Hershey Medical Center. And so there is a need for larger prospective studies utilizing Lumason in the more obese U.S. population.

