**7.1 Study Design**

Describe and explain the study design.

This is a prospective trial to determine if contrast enhanced ultrasound (CEUS) is non-inferior to CT or MRI in patients with hepatocellular carcinoma (HCC) following transcatheter arterial chemoembolization (TACE) treatments. All patients will receive standard of care CT/MRI and will also get a contrast ultrasound to directly compare.

Timepoint 0: You agree to take part in the study at the time of your first TACE treatment.

Timepoint 1:  
• CT or MRI and CEUS  
• Complete short survey

Timepoint 2: Return for follow-up standard of care imaging (either a CT or MRI).

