### 8.0 Subject Numbers and Statistical Plan

#### 8.1 Number of Subjects

Indicate the maximum number of subjects to be accrued/enrolled. Distinguish between the number of subjects who are expected to be enrolled and screened, and the number of subjects needed to complete the research procedures if applicable (i.e., numbers of subjects excluding screen failures.)

We plan to enroll 34 subjects.

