#### 8.2 Sample size determination

If applicable, provide a justification of the sample size outlined in section 8.1 to include reflections on, or calculations of, the power of the study.

Planned sample size = 34

Presently there is no data available to suggest how large an effect size may exert on the primary outcome measures. Accordingly, a formal sample size calculation was not done as the goal of this pilot study is to: 1) assess the feasibility of the study design, 2) generate data needed for a formal power calculation, and 3) generate pilot data for larger-scale grant submission. Based on the availability of patients, feasibility of our operations, we plan to recruit 34 patients. We believe this sample will serve our purpose well as a pilot study with plans to include further patients as funding allows.

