### 8.3 Statistical methods

Describe the statistical methods (or non-statistical methods of analysis) that will be employed.

Patient demographics and major clinical information described above will be summarized using descriptive statistics. The main outcome variables in primary objective are the incidence of residual tumor and new tumor, which are both binary. The rate of residual/new tumors using CEUS and CT/MRI will be compared using McNemar's test, which is suitable for comparing paired binary variables. The point estimate and 95% confidence interval (CI) of the incidence rate for CEUS and CT/MRI will be reported separately. Due to the limited sample size of this pilot study, the non-inferiority between CEUS vs CT/MRI will be evaluated just by comparing the CIs of the incidence rate for each method, not by a formal statistical non-inferiority test which requires a much larger sample size. A few additional subgroup analyses will be performed to see if the incidence rate varies by stratification (such as BMI group, liver disease type). Due to the exploratory nature of this study no multiple regression models will be used, and no adjustment of the alpha rate will be made due to multiple testing. Treating the CT/MRI as the clinical gold standard, the sensitivity and specificity of CEUS will be estimated with their 95% CIs. The data from secondary objective will be analyzed similarly as those for the primary objective. For tertiary objective, the subjective ratings from patients between the CT/MRI and ultrasound will be compared using nonparametric Wilcoxon Signed-rank tests. The ratings may be further correlated with some of the baseline demographic and clinical factors using nonparametric Kruskal-Wallis tests. All analyses will be performed using statistical software SAS version 9.4 or higher (SAS Institute, Cary, NC, USA). All tests are two-sided and the significance level to be used is 0.05.

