### 11.2 Potential Benefits to Others

Include benefits to society or others.

If CEUS is shown to be non-inferior to CT/MRI, there would be several different benefits to future patients (and potentially the subject themselves, in follow-up) –

This study has the potential to specifically affect patients with cirrhosis or other liver diseases who have been diagnosed and treated for HCC, often used as a bridge to transplantation. Four phase CT and contrast enhanced MRI are the standard methods for establishing the success of TACE treatment by looking for residual disease and for new tumor, but may be contraindicated or not feasible in certain patients. CEUS has a safer overall risk profile and is also significantly less expensive than CT or MRI. Contrast reactions are rare in CEUS, the exam has less contraindications than CT or MRI. Additionally, multiple separate doses can be administered in CEUS to get a second or better look at an area of concern in the liver.

Intrinsically, ultrasound has high spatial resolution and has a potential for identifying residual or recurrent tumor at the same rates and potentially even earlier than a CT scan can, where ethiodol can obscure subtle signs of residual tumor (23). This would ensure that HCC patients are triaged appropriately and potentially decreases morbidity with a safe, accurate, and less expensive bridge to liver transplantation.

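### Sections 1.1, 1.2 and 7.1 set out to determine non-inferiority, but sections 8.2 and 8.3 describe a 34-patient pilot with no margin, no calculation and no formal test; the aim should be restated as estimation

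*Combined protocol and SAP*

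**What the plan says.** Three places state the purpose as a determination of non-inferiority.

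- Section 1.1 opens: "we propose a prospective trial to determine if contrast enhanced ultrasound (CEUS) is non-inferior to CT or MRI".
- Section 7.1 describes the design in nearly the same words.
- Section 1.2 puts non-inferiority of CEUS to the routine CT/MRI at timepoint 1 first among the primary endpoints.

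The formal primary objective, in the second paragraph of 1.1, is more modest. It is to estimate the sensitivity and specificity of CEUS and to evaluate non-inferiority against CT/MRI.

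Section 8 describes a different kind of study. Section 8.2 gives "Planned sample size = 34", calls the study a pilot, and reports no formal calculation because "Presently there is no data available to suggest how large an effect size may exert on the primary outcome measures". Section 8.3 says non-inferiority will be judged only by setting the separate 95% intervals for the CEUS and CT/MRI incidence rates side by side, "not by a formal statistical non-inferiority test which requires a much larger sample size". Neither section gives a margin or a rule for reading that comparison. Section 8.3 also commits to sensitivity and specificity with 95% intervals, taking CT/MRI as the reference, but names no interval method.

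**The concern.** The objective and first primary endpoint fix what the trial may claim when it reports. Here they promise a yes-or-no answer on non-inferiority, while section 8 provides nothing that could give one and concedes that a proper test needs many more patients. The word pilot does not appear in 1.1, 1.2 or 7.1.

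Suppose CEUS misses none of 17 CT/MRI-positive patients. Under the stated aim this could be written up as non-inferiority determined, although the interval would still allow about one tumour in five to be missed. The comparison in 8.3 adds to the risk, because overlapping intervals in a sample of this size are easily taken for equivalence.

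**Working it through.** **Inputs from the document**
- 34 enrolled (8.1, 8.2), with no separate number of evaluable patients. Section 3.3.1 removes patients whose lesion is not visible on grayscale or who do not return for CT/MRI, so fewer than 34 may be analysed.
- Two-sided 0.05 and 95% intervals (8.3).

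**Assumptions, because the document is silent**
- A margin of 10 points, used only as a benchmark.
- Exact (Clopper-Pearson) limits, unless stated otherwise.
- 10, 17 or 24 CT/MRI-positive patients out of 34.

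**Step 1: the plan's own figure.** The number 34 rests on patient availability and feasibility. There is no formula behind it to reproduce.

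**Step 2: best case for sensitivity or specificity at timepoint 1.** CT/MRI is the reference, so the best CEUS can do is make no error. With n correct out of n, the exact two-sided 95% lower limit L solves L^n = 0.025, so L = 0.025^(1/n).

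| n in the group, no errors | Lower limit | Shortfall not excluded |
|---|---|---|
| 10 | 69.2% | 30.8 points |
| 17 | 80.5% | 19.5 points |
| 24 | 85.8% | 14.2 points |
| 34 | 89.7% | 10.3 points |
| 36 | 90.3% | 9.7 points |

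The smallest n with a limit above 90% is 36. With two misses in 17 (15/17), the exact interval is 63.6% to 98.5%.

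**Step 3: both measures together.** Sensitivity uses only the positives and specificity only the negatives, and the two groups add up to at most 34. The error-free number needed in each group to exclude 10 points depends on the interval:

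| Interval | Each group | Total |
|---|---|---|
| Exact, two-sided 95% | 36 | 72 |
| Wilson, two-sided 95% | 35 | 70 |
| Exact, one-sided 95% | 29 | 58 |
| Jeffreys, two-sided 95% | 24 | 48 |
| Jeffreys, one-sided 95% | 18 | 36 |

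Every total exceeds 34. At this assumed margin and with any of these intervals, no split of the 34 excludes the shortfall for both measures.

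**Step 4: the comparison in 8.3.** Take CT/MRI positive in 17/34 (assumed): 50%, exact 95% interval 32.4% to 67.6%. The lowest CEUS count whose interval still reaches 32.4% is 6/34: 17.6%, interval 6.8% to 34.5%. The difference is (17 − 6)/34 = 32.4 points, and the intervals overlap. Overlap therefore cannot support non-inferiority.

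**The case against.** **The plan already says it is a pilot.** Sections 8.2 and 8.3 are open about this. The formal objective already speaks of estimation, and the reported intervals would show the imprecision. All of this is true, and it means nothing is concealed. It does not settle which section governs: the opening of 1.1, the first endpoint and 7.1 still promise what section 8 disclaims.

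**The margin is not the plan's.** This stands. A reader might infer that 34 patients cannot support non-inferiority on any criterion, and the figures do not bear that out. Error-free results in all 34, or in 24, would exclude 15 points, and 17 out of 17 would just exclude 20. If all 34 are pooled in one group, the 10-point benchmark is missed by only 0.3 points. It is met with a one-sided 95% exact limit (91.6%) or a two-sided Jeffreys limit (92.9%).

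**Section 8.3 judges non-inferiority on incidence, not sensitivity.** On a paired difference in incidence, CEUS can exceed CT/MRI, and 1.1 expects that ethiodol may hide disease on CT. With 34 pairs and no discordance, the score lower limit is −3.84/(34 + 3.84) = −10.2 points. With one extra CEUS-positive and no CEUS-negative discordance, the score (Tango) limit is −7.5. So the limit in step 2 applies to sensitivity and specificity and not to every measure. But 8.3 plans no interval for the paired difference and no margin to hold it against.

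**Prior data.** A reader might infer that 2.1, with "The efficacy of CEUS in the post-TACE HCC population has been evaluated in the literature (2-14"), contradicts the statement in 8.2 that there is no data. It is in tension with it, no more. Section 2.1 gives no accuracy figures, and 2.1 and 2.3 explain why those studies do not carry over directly. The narrower point remains: an error-free precision figure needs no effect size, so lack of data does not explain its absence.

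**Section 11.2.** A reader might count this as another promise. It is conditional, "If CEUS is shown to be non-inferior to CT/MRI, there would be several different benefits to future patients", and does not say that this trial will show it.

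**Conclusion.** The point holds as a mismatch between the stated purpose and an acknowledged pilot. As designed, the trial cannot determine non-inferiority: it has no margin, no calculation, no formal test, and a substitute comparison that overlap can satisfy at a 32-point deficit.

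For the sensitivity and specificity named in 1.1, 36 positives and 36 negatives, all classified correctly, would be needed where at most 34 patients in total are available. That rests on an assumed 10-point margin and exact two-sided 95% limits. The 80.5% limit rests on an assumed 17/17 split. The overlap example rests on an assumed 17/34 positive on CT/MRI. The mismatch in wording depends on none of these.

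**What to change.** 1. **Sections 1.1 (opening sentence), 1.2 and 7.1:** replace the aim of determining non-inferiority with: *estimate, with 95% CIs, the sensitivity, specificity and paired agreement of CEUS against CT/MRI, to plan a non-inferiority trial.*
2. **Section 8.3:** state that no non-inferiority conclusion will be drawn from comparing or overlapping the separate intervals.
3. **Section 8.2:** replace the lack-of-data reason with the precision that 34 patients give over an assumed range of positives, for example error-free exact lower limits of 69%, 80.5% and 86% with 10, 17 and 24. No figures from the cited studies are needed.

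These are wording changes. They require no additional patients or procedures and fit the pilot purposes already listed in 8.2. The only cost is that the stated aim becomes more modest.

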### 1.2 Primary Study Endpoints

State the primary endpoints to be measured in the study.

Clinical trials typically have a primary objective or endpoint. Additional objectives and endpoints are secondary. The endpoints (or outcomes), determined for each study subject, are the quantitative measurements required by the objectives. Measuring the selected endpoints is the goal of a trial (examples: response rate and survival).

- Non-inferiority between CEUS and the patient's routine CT/MRI, which occurs 2-4 months after TACE treatment (Research timepoint 1). Additionally endpoints that will be measured include treated, residual, or new tumor present on the follow-up.
- The second routine follow-up of CT/MRI (timepoint 2) will be compared to exclude false positives/negatives in the first follow-up imaging (timepoint 1), which occurs approximately 2-months after the first imaging visit.
- Patient subjective data – through the use of a patient survey, given after the first follow-up (Research timepoint 1), where patient had CEUS and CT/MRI (2-4 months after TACE treatment).

### 1.3 Secondary Study Endpoints

State the secondary endpoints to be measured in the study.

To determine if patient or tumor characteristics (BMI, pre-treatment alpha feta protein levels, size of tumor treated) are predictive of whether CEUS is non-inferior to CT/MRI or in which cases it may not be, due to the limitations of ultrasound as a modality.

## 2.0 Background

### 2.1 Scientific Background and Gaps

Describe the scientific background and gaps in current knowledge.

For clinical research studies being conducted at Penn State Health/Penn State College of Medicine, and for other non-PSH locations as applicable, describe the treatment/procedure that is considered standard of care (i.e., indicate how patients would be treated in non-investigational setting); and if applicable, indicate if the study procedure is available to patient without taking part in the study.

Contrast-enhanced ultrasound (CEUS) has been in use globally for decades, but has only recently been approved for clinical use in the U.S. The accuracy of CEUS is similar to MRI and CT scans in establishing the diagnosis of hepatocellular carcinoma (HCC) in at risk-patients (1) and is being utilized with greater frequency to make this important diagnosis in patients with cirrhosis in the U.S.

One of several treatments for HCC is transcatheter arterial chemoembolization (TACE), with follow-up in 2-4 months - typically with either a CT or MRI. The efficacy of CEUS in the post-TACE HCC population has been evaluated in the literature (2-14) , which shows that it is reliable in diagnosing this entity via CEUS. However, some of the articles are with contrast agents not available in the US, some are in different patient populations than is common in the US (for example, hepatitis B is less common in the US than alcoholic cirrhosis, but the converse is true in most of the references studies, which were performed internationally) and should be replicated in the US population, and many of the articles were retrospective.

Over the last few years there has been slowly growing literature available in the U.S. patient population, in the form of case reports (15) or small (fewer than 20 patients) prospective studies (16, 17). But even these studies are not comparable with current CEUS practices, as both Shaw and Nam's small studies used Definity, a contrast agent approved in the U.S. that has low, but higher adverse events than Lumason (18) contrast agent, which is the standard contrast that is utilized at Penn State Milton S. Hershey Medical Center. And so there is a need for larger prospective studies utilizing Lumason in the more obese U.S. population.

### 2.2 Previous Data

Describe any relevant preliminary data.

In unpublished work (CATS IRB STUDY00014728) presented at the 2019 Society of Radiologists in Ultrasound annual national meeting, our group presented on our experience in imaging liver patients with CEUS (19). At the time of presentation, 62 patients had been imaged, with 16% yielding a positive finding. Our group correctly diagnosed all lesions – all malignant lesions and vascular thrombi had confirmation via gold standard imaging of CT or MRI, or on explanation; benign lesions were confirmed by stability on follow-up imaging. Our study also evaluated patient factors that resulted in limited visualization with CEUS, which included severe steatosis and/or increased abdominal adiposity. In addition, at our institution, we have utilized CEUS in several patients post-TACE, which were subsequently shown to correctly diagnosis residual tumor by follow-up MRI and/or TACE (unpublished). If one were able to accurately and reliably use CEUS to determine residual tumor after TACE, this would decrease the need for CT scans (which have the risk of radiation and contrast-enhanced nephropathy) and MRI scans (which are very expensive and are difficult to perform in patients with claustrophobia).

## 2.3 Study Rationale

### Provide the scientific rationale for the research.

These studies referenced above are not directly applicable to modern CEUS that is performed in the U.S. for the following reasons: 1) the contrast agents used in several studies are different from those available in the U.S. (2, 9, 13, 14) and 2) several of the studies are at least a decade old, and during the last ten years there have been advances in ultrasound imaging quality (10-14). In addition, many of the studies included small sample sizes, with fewer than 30 patients enrolled in the studies (5, 8, 10, 12, 14). Additionally, these results may not be generalizable to the U.S. patient population, as the vast majority of the prospective studies that directly compared CEUS to MRI or CT looked at patient populations outside of the U.S. (2-14). Worldwide (and particularly in Asia where most of these studies have been done), Hepatitis B is the most common etiology of cirrhosis and HCC, but in the U.S. this is not a common etiology. In the U.S. there are more patients with fatty liver disease, which has implications for affecting the accuracy and quality of the CEUS given the increased abdominal adiposity. In addition, with different etiologies of cirrhosis, the patients that develop HCC may have different tumor biology. HCC identification has been proven in the U.S. literature, but evaluation of HCC post TACE treatment has not in robust trials.

If CEUS is demonstrated to be non-inferior to MRI or CT, its use could result in overall cost savings to the patient and healthcare system, decreased radiation exposure, and decreased risk of contrast induced nephropathy from iodinated contrast agents. Ultrasound is significantly less expensive than MRI or CT, and does not expose patients to radiation as in the four phase CT required in screening for HCC. MRI requires screening to ensure safety of entering the scanning room, due to the strong magnetization that is utilized in generating images, and cannot be utilized in patients with pacemakers or automated implantable cardioverter defibrillators (AICDs), which are becoming more prevalent in our aging population. The bore of the magnet is small and patients may suffer issues with claustrophobia, which are not concerns in CEUS. Patient comfort may also be improved as the consistent breath hold required for CT and MRI to be diagnostic is not necessary in CEUS. The contrast used in ultrasound has a safer risk profile than CT dye (18, 20, 21) and severe contrast reactions are rare with ultrasound-based contrast agents. Long term deposition of MRI contrast in the brain has been reported in patients, and the lasting effects of this are currently unknown (22). Additionally, ultrasound contrast is not excreted through the kidneys, so renal function or risk of subsequent renal damage is not of concern. There will also be further decreases in the hidden costs of CT scan and MRI as it is standard of care to check a serum creatinine prior to a CT scan or MRI, and if the creatinine is elevated, there will be a need for intravenous hydration before and after the exam.

